5.1 Description

The DC-Stimulator MC (neuroConn, GmbH, Ilmenau, Germany) will be used to deliver the rtACS protocol. It can be classified a Category B, Class II non-significant risk medical device. It has the capacity to deliver the established rtACS protocol documented in previous efficacy, safety, and interventional studies. It is a multi-channel electrotherapy device consisting of a programmable waveform generator that connects to electrodes to deliver a non-invasive, weak electric current (see section 1.2).

5.2 Treatment Regimen

After obtaining written informed consent, participants will be allocated (1:1 ratio) to either rtACS or sham stimulation intervention group. The intervention protocol for each group involves 10 daily sessions delivered over 2 weeks, 1 session per day, < 60 minutes of continuous/sham stimulation (0-100 Hz) per day following the established dose parameters. The rtACS group will receive the stimulation dose per protocol. During a sham stimulation session, the DC-Stimulator MC will be programmed accordingly which may include brief periods of stimulation at the beginning and/or end of the session, serving to

CONFIDENTIAL

This material is the property of the NYU School of Medicine and Langone Medical Center. Do not disclose or use except as authorized in writing by the study sponsor

mimic the effects of a true stimulation session. Researchers report this is necessary to designing the masking component of this study.

5.3 Method for Assigning Subjects to Treatment Groups

For the randomization scheme, participants will be randomized (1:1 ratio) to the rtACS and sham stimulation groups using blocked randomization stratified by Centers (to determine any differences between the Centers). Random varying block sizes will be used to balance group allocation and minimize the risk of unmasking group assignment, and a randomization table will be computer generated accordingly. A statistician will generate a randomization table and a research staff member indirectly involved in the conduct of this study will conduct the process of allocation. Participants will be assigned in the order that they are enrolled. The randomization and allocation concealment will be uploaded to a secure database.

5.4 Subject Compliance Monitoring

Research personnel will monitor and document participants' compliance with attendance at scheduled baseline assessments, daily intervention sessions, and follow-up assessments. As part of the recruitment process, patients will be interviewed in regard to their availability to attend 10 daily sessions over a 2-week period. Participants' baseline assessments will be scheduled to accommodate their schedule within reason and the timeframe for the conduct of this study. In the event when an enrolled participant is unable to adhere to the study protocol, consideration for withdrawal will be discussed and documented by the research team.

5.5 Prior and Concomitant Therapy

During the study, participants will continue their normal glaucoma treatment regimen prescribed by their physician. Any change in said regimen or clinical procedures will be evaluated based on the eligibility criteria for this study.

5.6 Packaging

N/A. The DC-Stimulator MC device will be owned by NYULMC Department of Ophthalmology and will be used for this study for all participants at NYU Langone Eye Center. The device is treated like any patient-care instrument used within the department. Therefore, there are no individual packaging or kits for each participant. Each participant will have their own set of electrodes that will be managed per protocol (i.e., setup and cleaning), kept in individually labeled and sealed storage vessels, and will be stored in a research-designated space. In the event of device malfunction, a back-up device and extra electrodes will be stored onsite to avoid disruption of the study procedures.

5.7 Masking of Study

Interventionist will be masked to rtACS versus sham stimulation intervention group. He/she will not be involved in the allocation process. The DC-Stimulator MC has a programmable sham feature to maintain masking. A trained personnel who is not involved in data collection or analysis will be involved in the setup of the DC-Stimulator MC according to group allocation and rtACS protocol for each participant, following setup parameters and current standards for masking. Participants will be blind to group allocation. Following completion of the 10 daily sessions, interventionist and participants will be asked to guess the assigned condition during follow-up assessments.

5.8 Receiving, Storage, Dispensing and Return

5.8.1 Receipt of Study Device

The DC-Stimulator MC will be purchased and shipped from neuroCare Group GmbH, [name] to NYU Langone Eye Center, [name]. Upon receipt of the device (including backup device), an inventory will be performed and designated staff will verify that the shipment contains all the items noted in the shipment inventory. Any

CONFIDENTIAL

This material is the property of the NYU School of Medicine and Langone Medical Center. Do not disclose or use except as authorized in writing by the study sponsor

damaged piece in a given shipment will be reported to research personnel and documented. The DC-Stimulator MC will be used for this study for all participants at NYU Langone Eye Center.

5.8.2 Storage

The devices and supplies will be located in a treatment room designated for research purposes at NYU Langone Eye Center. The backup device will be appropriately placed for storage in a locked room.

6 Study Procedures

Screening procedures will be conducted in a research-designated room at the Centers appropriate for the setup and confidentiality for the interview procedures. Baseline assessments, intervention sessions, post-intervention and follow-up assessments for all participants will be conducted in a research-designated room at NYU Langone Eye Center.

Per standardized assessment guidelines and in order to accommodate and minimize the amount of time subjects may be willing and/or able to participate in research procedures at the Eye Center, assessments of functional ability and QoL may be coordinated with subjects for virtual administration (e.g., via phone, Webex, etc.).

The IRB-approved recruitment script used during the screening procedures for this study will be used for contacting new patients, in conjunction with the COVID-19 Updates Research Participant Recruitment script provided by the OSR/IRB. In addition, the applicable COVID information sheet for potential and enrolled subjects will be provided in the appropriate situation and while they are applicable to subjects.

Trained personnel who are not involved in data collection or analysis will be involved in the programming of the DC-Stimulator MC according to group allocation for each participant and the masking procedures that distinguish the delivery of rtACS versus sham stimulation. All intervention procedures will be conducted the same for both groups (rtACS and sham). Adverse events/adverse effects will be assessed in either condition.

Refer to Attachment 5 for the study schedule of events and Attachment 6 for documentation forms described below.

6.1 Visit: Baseline

Within five business days prior to the start of intervention sessions, the informed consent procedures and baseline assessments will be administered.

6.1.1 Process of Consent

Trained research personnel will review the consent form with the patient and explain the purpose of the study, the procedures, as well as risks and benefits.

- Review study requirements
- Allow patient to read consent
- Answer questions
- Patient will sign consent

A copy of the consent form will be given to the patient. All questions will be addressed before acquiring a patient's signed consent. The signed consent form will be placed in the Regulatory Binder, kept separate from participant data. The consent process will be documented on the Case Report Form. Each participant will be asked whether they wish to receive documentation linking them to the study.

6.1.2 Assessments

Ophthalmic examination: Procedures follow standard practice including examination by an ophthalmologist and testing includes: recording medical and family history, VA testing, axial length, IOP and central corneal thickness measurements, slit lamp examination, indirect ophthalmoscopy, and

CONFIDENTIAL

This material is the property of the NYU School of Medicine and Langone Medical Center. Do not disclose or use except as authorized in writing by the study sponsor

stereophotography of the optic nerve head, macula, and nerve fiber layer. The total time requirement for the ophthalmic examination is approximately 45 minutes.

The following assessments (approximate minutes to complete) will be administered at baseline: Pre-/Post-session Questionnaire (5), VF (20), VA (5), CS (5), OCT (10), OCT-A (10), VEP and PERG (15), Demographic Questionnaire (15), Verbal Fluency Test (5), Digit Span (5), LIFE-H (30), MNRead (10), VFQ-39 (25), SF-36 (25), and PSQI (10).

The total time requirement for participants for baseline testing is approximately 3 hours in addition to the ophthalmic examination.

MRI testing will be performed at baseline and will require up to 2 hours. Baseline assessments may be scheduled on separate days due to timing, location of MRI facility, and patient scheduling.

The Brief COPE questionnaire (Attachment 10) will be included in the battery of questionnaires. The Brief COPE is a 28-item questionnaire designed to measure effective/ineffective coping in response to a stressful life event. The time requirement for the questionnaire is less than 5 minutes. The questionnaire is included in order to capture effective/ineffective ways subjects cope with the COVID-19 situation and in order to determine whether their response to their lived experience with the COVID-19 situation may influence other study outcomes. The Brief COPE has been validated.^{155,156}

Pittsburgh Sleep Quality Index (PSQI) will be included in the battery of questionnaires. The PSQI is a validated 10-item questionnaire designed to measure sleep quality. Evidence suggests RGCs are involved in circadian photoreception to regulate homeostasis; modulating a non-visual response to light associated with sleep. Testing will be administered per standardized protocol and will require < 10 minutes to perform. For subjects who have completed research procedures through follow-up, we will contact them to conduct the questionnaire.

6.2 Visit: Daily intervention sessions 1-10

Beginning on a Monday, 10 daily intervention sessions will be scheduled to span 2 weeks (excluding the weekend). Prior to each daily session on the same date, trained personnel will check the DC-Stimulator MC and other necessary equipment that will be used during the session for quality and integrity of function (see Research Activity Checklist). The Pre-/Post-session Questionnaire will be completed (5 minutes). The stimulation protocol (rtACS or sham) will be delivered, requiring approximately 90 minutes including all associated procedures including setup.

The total time requirement for participants for daily sessions is approximately 1 hour.

6.3 Visit: Post-intervention

Post-intervention assessments will be scheduled for administration within five business days of participants' last intervention sessions.

Ophthalmic examination: Procedures follow standard practice including examination by an ophthalmologist and testing includes: recording medical and family history, VA testing, axial length, IOP and central corneal thickness measurements, slit lamp examination, indirect ophthalmoscopy, and stereophotography of the optic nerve head, macula, and nerve fiber layer. The total time requirement for the ophthalmic examination is approximately 45 minutes.

The following assessments (approximate minutes to complete) will be administered: Pre-/Post-session Questionnaire (5), VF (20), VA (5), CS (5), OCT (10), OCT-A (10), VEP and PERG (15), Verbal Fluency Test (5), Digit Span (5), LIFE-H (30), MNRead (10), VFQ-39 (25), SF-36 (25), and Post-intervention Interview (60).

The total time requirement for participants for post-intervention testing is 3 hours in addition to the ophthalmic evaluation.

CONFIDENTIAL

This material is the property of the NYU School of Medicine and Langone Medical Center. Do not disclose or use except as authorized in writing by the study sponsor

MRI testing will be performed at post-intervention and will require up to 2 hours. Post-intervention assessments may be scheduled on separate days due to timing, location of MRI facility, and patient scheduling.

The Brief COPE questionnaire (Attachment 10) will be included in the battery of questionnaires. The Brief COPE is a 28-item questionnaire designed to measure effective/ineffective coping in response to a stressful life event. The time requirement for the questionnaire is less than 5 minutes.

6.4 Visit: Follow-up

Follow-up assessments will be scheduled for administration 4 weeks following the participants' last intervention sessions.

Ophthalmic examination: Procedures follow standard practice including examination by an ophthalmologist and testing includes: recording medical and family history, VA testing, axial length, IOP and central corneal thickness measurements, slit lamp examination, indirect ophthalmoscopy, and stereophotography of the optic nerve head, macula, and nerve fiber layer. The total time requirement for the ophthalmic examination is approximately 45 minutes.

The following assessments (approximate minutes to complete) will be administered: Pre-/Post-session Questionnaire (5), VF (20), VA (5), CS (5), OCT (10), OCT-A (10), VEP and PERG (15), Verbal Fluency Test (5), Digit Span (5), LIFE-H (30), MNRead (10), VFQ-39 (25), and SF-36 (25).

The total time requirement for participants for follow-up testing is approximately 3 hours in addition to the ophthalmic examination.

MRI testing will be performed at follow-up and will require up to 2 hours. Follow-up assessments may be scheduled on separate days due to timing, location of MRI facility, and patient scheduling.

The Brief COPE questionnaire (Attachment 10) will be included in the battery of questionnaires. The Brief COPE is a 28-item questionnaire designed to measure effective/ineffective coping in response to a stressful life event. The time requirement for the questionnaire is less than 5 minutes.

7 Statistical Plan

7.1 Sample Size Determination

Given the objectives of this pilot study (see section 2) and limited data about the effect of rtACS for people with glaucoma, we estimate to enroll 16 participants to complete the study protocol. Our rationale for this number includes the following considerations: feasibility, quantifying an estimate of effect and estimate of variance, and validating methodologies.¹⁵³ We are using a block randomization scheme with a 1:1 allocation ratio for rtACS versus sham stimulation groups to collect data to inform the characterization of each group. We anticipate finding little to no effects in the sham stimulation group for a control but we establish equal allocation to groups to assess potential placebo effect.

7.2 Statistical Methods

All study participants will be included in efficacy analyses as randomized (intent to treat population). Treatment effects on all outcomes will be estimated with 95% confidence interval. Supportive analyses will include estimating effects in study participants who received at least five sessions of their randomized assigned treatment as supportive analyses and hypothesis testing with two-sided tests at significance level of 0.05.

The primary outcome variables that will be evaluated in this study are structure and function of the retina and visual pathway (using imaging and electrophysiological technology), visual function, functional ability,

CONFIDENTIAL

This material is the property of the NYU School of Medicine and Langone Medical Center. Do not disclose or use except as authorized in writing by the study sponsor

and QoL. Secondary outcome variables include feasibility of procedures and methodologies for recruitment, enrollment, data collection and data management.

Subjective demographic and clinical characteristics will be analyzed using descriptive statistics. Continuous variables will be described by means and standard deviations (or by median and interquartile range for skew distribution) and categorical variables will be described by frequencies (count) and percentages. Overall, to analyze our aims and test our hypotheses we will use between and within group comparison analyses (e.g., *t*-tests) to evaluate change scores from baseline to post-intervention and follow-up between rtACS and sham stimulation groups. We will use effect size calculations to evaluate the magnitude of differences between and within groups. Additionally, we will quantify an estimate of variance using 95% confidence interval. Analyses will be conducted using R statistical computing software.

Aim 1 (2.1.1.1): Measure structural and functional capabilities of neuronal physiology and reorganization of the visual pathway (from eye to visual brain)

We will calculate change scores between baseline and study end scores on primary outcome variables. These difference scores will then be described and compared between and within groups for: 1) structure and function of the retina and visual pathway measures and 2) visual function. We will perform a multivariate analysis to examine the correlation between measures of retinal and visual pathway structure/function and measures of visual function. We will quantify estimates of effect and estimates of variance.

Aim 2 (2.1.2.1): Measure objective ability/disability and subjective well-being (i.e., QoL)

We will perform a multivariate analysis to examine the correlation among measures of visual function, functional ability, and QoL.

Aim 3 (2.2.1.1): Evaluate the data collection, data management methods, and study procedures for targeted outcomes other than the primary objectives

We will use descriptive statistics to analyze secondary outcomes to measure feasibility of procedures and methodologies for recruitment, enrollment, data collection and data management, etc.

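### Do the hypothesis tests and unspecified multivariate correlations in section 7.2 need rewriting for a 16-person pilot?

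*Combined protocol and SAP*

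**What the plan says.** Section 7.2 opens with the intention-to-treat population and then says: "Treatment effects on all outcomes will be estimated with 95% confidence interval". Testing comes next, in a sentence about supportive analyses that ends "as supportive analyses and hypothesis testing with two-sided tests at significance level of 0.05". This is the only significance level in the plan.

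The following paragraph begins "The primary outcome variables that will be evaluated in this study are structure and function of the retina and visual pathway" and goes on to add visual function, functional ability and quality of life. None is ranked first.

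After the descriptive statistics comes the sentence at issue: "Overall, to analyze our aims and test our hypotheses we will use between and within group comparison analyses", with t-tests in brackets as an example, "to evaluate change scores from baseline to post-intervention and follow-up between rtACS and sham stimulation groups". Effect sizes and 95% confidence intervals follow directly.

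Under Aim 1 the plan says "We will calculate change scores between baseline and study end scores on primary outcome variables". It compares the differences for two domains (retinal and visual-pathway structure and function, and visual function) and adds: "We will perform a multivariate analysis to examine the correlation between measures of retinal and visual pathway structure/function and measures of visual function". Under Aim 2 it says only: "We will perform a multivariate analysis to examine the correlation among measures of visual function, functional ability, and QoL".

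Section 7.1 sets the number at 16, allocated 1:1, on grounds of feasibility, estimating effect and variance, and validating methods. The Study Summary lists descriptive statistics, multivariate analyses and estimates of effect and variance. It does not list hypothesis testing.

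**The concern.** Read alone, the sentence on testing hypotheses turns an estimation pilot into an efficacy test. The hypotheses in section 2 concern efficacy and association, not feasibility. The comparisons are both between and within groups, at two visits, across domains that are all primary. With no lead measure, chance findings are likely and real effects are mostly missed.

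The two correlation analyses look looser still. Section 3.2 lists instruments by domain, but nothing says which measures enter, which technique is used, or whether the arms are pooled. Some multivariate methods applied to 16 people would show strong agreement between pure-noise variables.

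The pilot is meant to inform a multi-site trial (sections 2.1 and 2.2). If a measure were chosen or sized because it reached p<0.05 here, the larger trial could rest on an exaggerated effect.

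**Working it through.** There is no power calculation to reproduce. The inputs are 16 participants at 1:1, nominally 8 per arm (section 7.1), two-sided 0.05 (section 7.2), and effects of 0.51 to 0.67 from an earlier sham-controlled trial in optic nerve impairment (section 1.1.4), taken here as standardised differences. The number of tests and the correlations between measures are assumptions, because the documents give neither.

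**Threshold.** With 14 degrees of freedom the critical t is 2.145. The smallest significant difference is 2.145 × √(2/8) = 2.145 × 0.5 = 1.07 SD. This is also the half-width of the 95% interval, in units of the pooled SD.

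**Power.** The noncentrality is d × √(8/2) = 2d. At d = 0.51 (noncentrality 1.02) power is 15.8%. At d = 0.67 (1.34) it is 23.9%.

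**Exaggeration among significant results (simulated).**

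| True d | Mean absolute standardised estimate ÷ truth |
|---|---|
| 0.51 | 2.8 |
| 0.67 | 2.2 |
| 0.8 | 1.9 |
| 1.0 | 1.5 |
| 1.5 | 1.2 |

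Measured in true SD units, the ratio at 0.67 is 1.9. A doubling is therefore not general; it depends on the true effect being modest.

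**False positives.** Section 3.2.1 explicitly lists 3 OCT measures, 2 VEP, 1 PERG and 4 of visual function (mean deviation, near acuity, far acuity, contrast sensitivity), making 10. OCT-A and MRI are left out because their number of summary measures is not fixed. If the 10 are independent, the chance of at least one p<0.05 at one visit is 1 − 0.95^10 = 40%. Simulated results with no true effect:

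| Tests | Correlation 0 | 0.5 | 0.8 |
|---|---|---|---|
| Between arms, one visit | 40% | 30% | 18% |
| Between arms, two visits (change scores correlated 0.5) | 62% | 48% | 31% |
| One visit plus within-group tests in both arms | 71% | 58% | 39% |

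**Correlations, n = 16.** A single correlation must exceed 0.497 in absolute value for p<0.05. An observed 0.5 has a 95% interval of tanh(0.549 ± 1.96/√13) = 0.01 to 0.80. For 6 structural or electrophysiological measures against 4 visual-function measures, the median first canonical correlation between independent normal variables is about 0.87. That applies only if canonical correlation is used, and the plan does not name it.

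**The passages side by side.** The only stated significance level sits under the supportive analyses. The unlabelled sentence gives no level, offers t-tests as one example, and is followed by effect sizes and intervals. The aim-specific text plans group comparisons for two domains; for functional ability and quality of life, Aim 2 plans only correlation. Section 3.2.2 frames those two domains as assessing whether the procedures are feasible. No section makes a decision about the later trial depend on a p-value.

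**The case for a change.** The strongest case for a change is that the supportive label appears once and a later sentence omits it, so a reader cannot be sure whether tests support the estimates or decide the hypotheses. Leaving the correlation method and variables open also allows both to be chosen after the data are seen. Even the most favourable one-visit case above, 18%, is over three times the nominal 5%. Adding a label and naming a method would be cheap.

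Some of this stands. The label is missing, and the correlation analyses are specified only by domain. A reader should treat any significant result or high correlation as exploratory. But the general sentence is naturally read in the light of the paragraph before it, and the estimates and intervals are sound whether or not the word is added.

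Stronger remedies carry a cost. Dropping the tests removes something already described as supportive. Replacing the multivariate analyses with a short list would cover the second and third hypotheses less broadly, and the team would still have to choose the list. Formal multiplicity control is not needed in a feasibility pilot of this size.

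**Conclusion.** The concern describes the text accurately and its main figures reproduce, but it does not call for a change. The plan already reports what a pilot of 16 can support: effects with 95% intervals on all outcomes, effect sizes and variances. What is left is one sentence without a label and two exploratory analyses whose detail the analyst will settle. The Aim 1 reference to study end, where the general text names two visits, is a clerical looseness.

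The size of the limitation is worth keeping in mind when the results are read. A difference below 1.07 SD will not be significant, and power is 16% to 24% if effects of 0.51 to 0.67 applied. That range comes from high-resolution perimetry in optic nerve impairment, which is not a measure in this trial, so it is context only. The false-positive figures rest on assumed test counts and correlations.

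The conclusion rests on the tests being read as supportive, as section 7.2 first describes them. It would be different if a later document used p-values from this pilot to select or size the endpoints of the multi-site trial.

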1.3.3 Potential Benefits

rtACS has been associated with improved visual function and QoL in people with visual impairment resulting from optic neuropathy.⁹⁹ In addition to the potential benefits of improved visual function and QoL, we will explore the potential benefits of rtACS in regard to participants' functional ability. We anticipate no direct benefit from sham rtACS in regard to visual function, QoL, and functional ability.

2 Study Objectives

In this proposed pilot study, we will assess the feasibility of procedures that are key to the conduct of a multi-site randomized controlled trial to explore the influence of rtACS versus sham stimulation on neuronal morphology and physiology to improve people's visual function, functional ability, and QoL. The expected outcomes (hypotheses) for this project are that (1) rtACS activates viable but poorly or non-functional RGCs to improve their structural and functional capabilities, (2) measures of retinal, ON, and visual brain structures and function will correspond with improvement in visual function, and (3) changes in visual function following rtACS will be associated with improvements in participants' functional ability and QoL.

CONFIDENTIAL

This material is the property of the NYU School of Medicine and Langone Medical Center. Do not disclose or use except as authorized in writing by the study sponsor

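### Section 7.2 lets within-arm change be used to test whether rtACS works; inference should rest on the rtACS-versus-sham contrast alone, preferably adjusted for baseline and Center

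*Combined protocol and SAP*

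**What the plan says.** Sections 2.1.1 and 2.1.2 frame both primary objectives as rtACS relative to sham. Section 7.2 opens with estimation in the population as randomised: "Treatment effects on all outcomes will be estimated with 95% confidence interval". Among the supportive analyses it lists "hypothesis testing with two-sided tests at significance level of 0.05".

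Further on, Section 7.2 says that "to analyze our aims and test our hypotheses we will use between and within group comparison analyses", with t-tests as the example, "to evaluate change scores from baseline to post-intervention and follow-up between rtACS and sham stimulation groups". It adds: "We will use effect size calculations to evaluate the magnitude of differences between and within groups". For Aim 1 it says of the change scores: "These difference scores will then be described and compared between and within groups for" the structural measures and visual function. The Study Summary likewise pairs between-group and within-group analyses.

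The hypotheses in Section 2 are about effect. The first is that "rtACS activates viable but poorly or non-functional RGCs to improve their structural and functional capabilities", and it names no comparator. Section 7.1 explains the 1:1 allocation: "we establish equal allocation to groups to assess potential placebo effect". It also expects little or no change under sham. Section 3.3.1.3 includes two cognitive tests because better performance after the intervention might reflect attention instead of the intervention.

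No baseline covariate is named, and the randomisation stratum (Center, Section 5.3) does not appear in the analysis text.

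**The concern.** Describing how each arm changed suits a pilot that wants to characterise both groups. Testing a hypothesis about rtACS with the change in the rtACS arm alone is different. That change is the sum of any treatment effect and whatever would have happened under sham. The protocol itself names two contributors to the second part: placebo response (Section 7.1) and, for performance measures, attention (Section 3.3.1.3). Only the contrast with sham removes them.

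Section 7.2 lists both kinds of comparison as ways to test the hypotheses and does not rank them. A report could therefore cite a significant rtACS-arm change, or a significant rtACS arm beside a non-significant sham arm, as support for the first hypothesis and still be within the plan. The within-group effect sizes carry the same risk. If both arms change equally, the within-arm effect size equals the shared change although the treatment effect is zero. Section 7.1 gives an estimate of effect as one reason for the sample size, so a within-arm figure could be carried into the design of the larger trial.

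**Working it through.** **Inputs from the plan.** Sixteen participants at 1:1 (Section 7.1), so 16 / 2 = 8 per arm. Two-sided 0.05 and t-tests on change scores (Section 7.2). Section 7.1 gives no power, effect size, SD or target precision, so there is no sample-size calculation to reproduce.

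**Assumed, because the documents give no value.** Shared change δ, in SDs of the change score: 0 to 0.8. Baseline-to-post correlation r: 0.3 to 0.95. Normal outcomes and complete data throughout.

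**1. Within-arm test with no treatment effect.** Both arms have mean change δ. The one-sample t statistic has 7 degrees of freedom, noncentrality δ√8 and critical value 2.365:

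p = P(T > 2.365) + P(T < −2.365).

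The arms are independent, so the chance that rtACS is significant and sham is not equals p(1 − p). The between-arm difference is zero, so its test rejects in 5% of trials whatever δ is.

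| δ (SD) | δ√8 | rtACS arm significant | rtACS significant, sham not | Between-arm test significant |
|---|---|---|---|---|
| 0 | 0 | 5% | 5% | 5% |
| 0.1 | 0.28 | 6% | 5% | 5% |
| 0.2 | 0.57 | 8% | 7% | 5% |
| 0.3 | 0.85 | 11% | 10% | 5% |
| 0.5 | 1.41 | 23% | 18% | 5% |
| 0.8 | 2.26 | 50% | 25% | 5% |

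Example at δ = 0.5: p = 0.232, and 0.232 × 0.768 = 0.178. Simulation of 400,000 trials at δ = 0.3 / 0.5 / 0.8 agrees (0.101 / 0.179 / 0.250). In those discordant trials the between-arm test was significant in only 19% / 12% / 9%.

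**2. Does n = 8 cause this?** At δ = 0.3 and n = 20 per arm, p = 0.247 and 0.247 × 0.753 = 0.186. The discordant rate rises from 10% to 19%, so small arms are not the cause.

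**3. Precision of the between-arm contrast.** With equal variance σ² at both visits, the change score has variance 2(1 − r)σ². The post value adjusted for baseline has variance (1 − r²)σ². The adjusted-to-change ratio is (1 + r)/2, for example 0.75 at r = 0.5. In large samples the change-score interval would then be √(1/0.75) = 1.15 times as wide. With 16 people, adjusting for baseline and Center costs two degrees of freedom (14 to 12; t quantile 2.145 to 2.179) and requires the baseline slope to be estimated. Simulating 60,000 trials of 8 v 8 per value of r, with Centers split 4/4 in each arm and no Center effect, gives the ratio of mean interval widths:

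| r | 0.3 | 0.5 | 0.7 | 0.8 | 0.9 | 0.95 |
|---|---|---|---|---|---|---|
| Change-score width / adjusted width | 1.17 | 1.09 | 1.03 | 1.00 | 0.97 | 0.96 |

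Both methods were unbiased, with type I error of 4.8–5.2%.

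**The case against.** The strongest reply is that the comparator is already clear. Both primary objectives name sham. A treatment effect estimated as randomised most naturally means rtACS minus sham. The sentence that mentions within-group comparisons ends by pointing to the two groups. Tests are supportive, and describing each arm is a legitimate purpose of a pilot. All of this stands, and it makes the point one of wording and not a flaw in the lead analysis. It does not close the gap, because the sentence still names within-group comparisons as a means of testing the hypotheses and the Aim 1 text repeats the pairing. Leading with estimation does not protect the within-arm figures either: a within-arm 95% interval excludes zero in exactly the trials where the within-arm test is significant.

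A second reply is that Section 7.1 expects little or no sham change. That also stands. At a shared change of 0 to 0.2 SD, the discordant pattern appears in only 5% to 7% of trials. But the same section keeps a full sham arm because a placebo effect is possible, so the larger values cannot be ruled out in advance.

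Four stronger readings are tempting, and the documents do not support them:

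- That efficacy will be concluded from a significant rtACS arm beside a non-significant sham arm. The plan does not say so; its wording only leaves room for it.
- That the small arms create the problem. Step 2 of the working shows otherwise.
- That the visual field variability noted in Section 4.1 would move both arms. Random scatter is already in the standard error and produces no shared mean shift.
- That the two eyes of a participant will be analysed as independent. Section 7 is silent on the unit and proposes no such analysis.

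**Conclusion.** The point holds as a matter of wording that should be settled before analysis. Section 7.2 allows within-arm change to test hypotheses about the effect of rtACS, and nothing in the document confines it to description. If rtACS does nothing and both arms share a change of 0 to 0.8 SD, the rtACS-arm test is significant in 5% to 50% of trials, against 5% for the between-arm test. The range rests on an assumed shared change. Under the protocol's own expectation the truth lies near the low end, and the harm arises only if within-arm results are read as evidence of effect.

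The absence of baseline and Center adjustment is a lesser matter. With complete data the change-score contrast is unbiased and only precision is affected. The change-score interval is about 17% / 9% / 3% / 0% wider at r = 0.3 / 0.5 / 0.7 / 0.8, and the adjusted interval is about 3–4% wider at r = 0.9–0.95. The plan's mention of t-tests is an example, so adjustment is not excluded.

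**What to change.** In Section 7.2:

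1. State that all inference about an effect of rtACS rests on the between-arm estimate and its 95% interval, and that within-arm changes and effect sizes are reported as description only. Make the same change in the Aim 1 text. This costs nothing and needs no new data.
2. As a cheap improvement, estimate the between-arm contrast at each visit (post-intervention and 4 weeks) from a linear model of the post value on arm, baseline value and recruiting Center, in place of a t-test on change scores. This is a simple model in R on data already collected. The cost is two degrees of freedom and an interval about 3–4% wider if the baseline-to-post correlation is 0.9–0.95.

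While editing, add a line saying that the participant is the unit of analysis for eye-level outcomes. How the two eyes are combined or selected is the investigators' choice.
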